Data Analysis for Drug Repurposing for Effective Alzheimer's Medicines – Pentoxifylline vs Cilostazol

NCT05635370

July 7, 2023

1. Comparison Details

a. Intended aim(s)

To evaluate the comparative risk of dementia onset between patients treated with Pentoxifylline versus cilostazol for peripheral artery disease (PAD).

b. Primary endpoint

Incident dementia (i.e., Alzheimer's disease, vascular dementia, senile, presenile, or unspecified dementia, or dementia in other diseases classified elsewhere).

2. Person responsible for implementation

[name]

3. Data Source(s)

Medicare, 2008-2018

4. Study Design Diagrams

[figure not shown]
[figure not shown]

Figure- Alternate analysis approaches

[figure not shown]
■■■ Included person-time
 ■■■ Excluded person-time

Provides 'on treatment' estimates for the outcome risk and addresses exposure person-time misclassification

Analysis 1

[figure not shown]

Analysis 3

[figure not shown]

Addresses reverse causation due to preferential treatment initiation related to unrecorded cognitive impairment at study start and informative-censoring

Analysis 2

Analysis 4

5. Cohort Identification

a. Cohort Summary

This study will employ a new user, active comparator, observational cohort study design comparing Pentoxifylline versus Cilostazol. The patients will be required to have continuous enrollment during the baseline period of 365 days before initiation of study drugs (cohort entry/index date). Follow-up for the outcome (dementia) differs between analyses. Follow-up begins the day after drug initiation (analysis 1, 3, 4); 180 days after drug initiation (analysis 2).

b. Key details regarding cohort creation

Index date:

- Day of initiation of new Pentoxifylline versus Cilostazol use

Inclusion criteria for analyses 1, 3, 4:

- Aged \geq 65 years on the index date
- 365 days enrollment in Medicare Parts A, B, and D with no HMO coverage prior to index date
- No use of Pentoxifylline versus Cilostazol, any time prior to index date (all available lookback approach with a minimum of 365 days)
- No diagnosis of dementia any time prior to and including index date
- No history of nursing home admission recorded in any time prior to and including index date
- At least two claims with peripheral artery disease diagnosis recorded in 365 days prior to index date (ICD-9 or ICD-10 codes)¹

Inclusion criteria for analysis 2:

- Aged \geq 65 years on the index date

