- 365 days enrollment in Medicare Parts A, B, and D with no HMO coverage prior to index date
- No use of Pentoxifylline versus Cilostazol, any time prior to index date (all available lookback approach with a minimum of 365 days)
- No diagnosis of dementia any time prior to and including index date
- No history of nursing home admission recorded in any time prior to and including index date
- At least two claims with peripheral artery disease diagnosis recorded in 365 days prior to index date (ICD-9 or ICD-10 codes)¹

- 180-day continuous use of Pentoxifylline versus Cilostazol starting on the index date

c. Flowchart of the study cohort assembly

	Less Excluded Patients	Remaining Patients
All patients		23,466,175
Did not meet cohort entry criteria	-23,393,311	72,864
Excluded due to insufficient enrollment	-45,683	27,181
Excluded based on Dementia Exclusion	-6,100	21,081
Excluded based on Nursing Home Admission	-4,080	17,001
Excluded based on Peripheral artery disease Diagnosis	-4,524	12,477
Excluded anyone aged <65 at index	-2,079	10,398
Patients in Pentoxifylline group		1,701
Patients in Cilostazol group		8,697
Final cohort		10,398

6. Variables

a. Exposure-related variables:

Study drug:

The study exposure of interest is initiation of Pentoxifylline

Comparator:

Cilostazol

b. Covariates:

Demographics	
Age	Region
Gender	Calendar year of index date
Race	Low income subsidy

Dementia risk factors	
Diabetes	Depression
Obesity	Anxiety
Hypertension	Bipolar disorder
Coronary artery disease	Schizophrenia

Markers for healthy behavior, frailty, healthcare use	
Smoking	Number of hospitalizations
Mammography	Number of physician office visits
Colonoscopy	Number of serum creatinine tests ordered
Fecal occult blood test	Composite frailty score
Influenza vaccination	Number of C-reactive protein tests ordered
Pneumococcal vaccination	Osteoporosis
Herpes zoster vaccination	Fractures
Bone mineral density test	Falls
Number of distinct generic agents	Use of supplemental oxygen
Number of emergency room visits	Combined comorbidity score
Number of outpatient visits	

Comedication use	
Lithium	Diuretics
Anti-epileptic mood stabilizers	Nitrates
Anti-epileptics (other than mood stabilizers)	Lipid lowering drugs

Atypical antipsychotics	Non-insulin diabetes medications
Benzodiazepines	Insulin
Serotonin-norepinephrine reuptake Inhibitors	Antidepressants
Selective serotonin reuptake inhibitors	Angiotensin II receptor blockers (ARBs)

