For analysis 2, the follow-up will start 180 days after initiation of Pentoxifylline and Cilostazol and will continue until the earliest date of the following events:

- The first occurrence of the outcome of interest, unless otherwise specified for selected outcomes,
- The date of end of continuous registration in the database,
- End of the study period,
- Measured death event occurs,
- Maximum allowed follow-up time (1095 days) reached

7. Propensity score analysis

We will use a propensity-score (PS)²-based approach to account for measured confounding in this study. The PS will be calculated as the predicted probability of initiating the exposure of interest (i.e., the repurposing candidate) versus the reference drug conditional on baseline covariates using multivariable logistic regression constructed separately in each data source. On average, patients with similar PSs have similar distribution of potential confounders used to estimate the PS. Therefore, analyses conditioned on the PS provide effect estimates that are free from measured confounding. For all our analyses, initiators of each exposure of interest will be matched with initiators of the reference exposure based on their PS within each data source.³ Pair matching will be conducted using a nearest-neighbor algorithm, which seeks to minimize the distance between propensity scores in each pair of treated and reference patients,⁴ and a caliper of 0.025 on the natural scale of the PS will be used to ensure similarity between the matched patients.⁵

We report multiple diagnostics for PS analysis in this protocol. First, the PS distributional overlap is provided between two groups before and after matching to ensure comparability of these groups.⁶ Next, balance in each individual covariate between two treatment groups is reported using standardized differences.⁷

8. Table for covariate balance

Variable	Crude			PS-Matched		
	Pentoxifylline (N = 1,701)	Cilostazol (N = 8,697)	St. Diff	Pentoxifylline (N = 1,687)	Cilostazol (N = 1,687)	St. Diff
Demographics						
Age, mean (SD)	76.2 (7.3)	75.3 (6.9)	0.13	76.2 (7.2)	76.3 (7.2)	-0.01
Gender, n (%)						
Male	828 (48.7)	4733 (54.4)	-0.12	822 (48.7)	827 (49)	-0.01
Female	873 (51.3)	3964 (45.6)	0.12	865 (51.3)	860 (51)	0.01
Race, n (%)						
White	1386 (81.5)	7096 (81.6)	0.00	1377 (81.6)	1347 (79.8)	0.05
Black	156 (9.2)	935 (10.8)	-0.05	156 (9.2)	176 (10.4)	-0.04
Hispanic	70 (4.1)	237 (2.7)	0.08	67 (4)	65 (3.9)	0.01

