Other	89 (5.2)	429 (4.9)	0.01	87 (5.2)	99 (5.9)	-0.03
Region, n (%)						
Northeast; n (%)	274 (16.1)	1697 (19.5)	-0.09	272 (16.1)	288 (17.1)	-0.03
South; n (%)	795 (46.7)	3749 (43.1)	0.07	788 (46.7)	779 (46.2)	0.01
Midwest; n (%)	354 (20.8)	2069 (23.8)	-0.07	353 (20.9)	337 (20)	0.02
West; n (%)	273 (16)	1171 (13.5)	0.07	269 (15.9)	279 (16.5)	-0.02
Other; n (%)	5 (0.3)	11 (0.1)	0.04	5 (0.3)	4 (0.2)	0.01
Calendar year of index date, n (%)						
2014	444 (26.1)	2016 (23.2)	0.07	436 (25.8)	435 (25.8)	0.00
2015	338 (19.9)	1908 (21.9)	-0.05	336 (19.9)	310 (18.4)	0.04
2016	335 (19.7)	1713 (19.7)	0.00	335 (19.9)	349 (20.7)	-0.02
2017	303 (17.8)	1606 (18.5)	-0.02	300 (17.8)	296 (17.5)	0.01

DREAM study protocol - Comparison 12 Pentoxifylline vs Cilostazol

2018	281 (16.5)	1454 (16.7)	-0.01	280 (16.6)	297 (17.6)	-0.03
Low income subsidy, n (%)	464 (27.3)	2035 (23.4)	0.09	459 (27.2)	492 (29.2)	-0.04
Dementia risk factors, n (%)						
Anxiety	247 (14.5)	1090 (12.5)	0.06	245 (14.5)	236 (14)	0.02
Bipolar disorder	15 (0.9)	67 (0.8)	0.01	15 (0.9)	13 (0.8)	0.01
Coronary artery disease	800 (47)	4789 (55.1)	-0.16	792 (46.9)	790 (46.8)	0.00
Depression	240 (14.1)	1027 (11.8)	0.07	236 (14)	226 (13.4)	0.02
Diabetes	826 (48.6)	4211 (48.4)	0.00	819 (48.5)	852 (50.5)	-0.04
Hypertension	1512 (88.9)	8055 (92.6)	-0.13	1500 (88.9)	1502 (89)	0.00
Obesity	325 (19.1)	1373 (15.8)	0.09	321 (19)	308 (18.3)	0.02
Schizophrenia	2 (0.1)	8 (0.1)	0.01			0.00
Markers for healthy behavior, frailty, healthcare use						
Bone mineral density test, n (%)	141 (8.3)	725 (8.3)	0.00	139 (8.2)	130 (7.7)	0.02
Colonoscopy, n (%)	143 (8.4)	861 (9.9)	-0.05	141 (8.4)	148 (8.8)	-0.02
Fecal occult blood test, n (%)	132 (7.8)	696 (8)	-0.01	131 (7.8)	131 (7.8)	0.00
Influenza vaccination, n (%)	1035 (60.8)	5419 (62.3)	-0.03	1026 (60.8)	978 (58)	0.06
Mammography, n (%)	281 (16.5)	1455 (16.7)	-0.01	279 (16.5)	283 (16.8)	-0.01
Pneumococcal vaccination, n (%)	652 (38.3)	3612 (41.5)	-0.07	649 (38.5)	621 (36.8)	0.03
Smoking, n (%)	599 (35.2)	3881 (44.6)	-0.19	595 (35.3)	580 (34.4)	0.02
Number of C-reactive protein tests ordered, mean (SD)	0.3 (1.2)	0.2 (0.7)	0.13	0.3 (0.9)	0.3 (1)	-0.02
Number of emergency room visits, mean (SD)	0.8 (1.4)	0.7 (1.3)	0.08	0.7 (1.4)	0.7 (1.4)	0.00
Number of distinct prescriptions, mean (SD)	13.9 (6.7)	12.4 (5.9)	0.23	13.7 (6.6)	13.8 (6.7)	0.00

DREAM study protocol - Comparison 12 Pentoxifylline vs Cilostazol

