Other PAD treatments and PAD severity indicators , n (%)						
Critical limb ischemia	394 (23.2)	1058 (12.2)	0.29	381 (22.6)	380 (22.5)	0.00
Thrombolytic therapy	10 (0.6)	26 (0.3)	0.04	9 (0.5)	6 (0.4)	0.03
Number of cardiologist visits, mean (SD)	3.5 (5.9)	4 (5.2)	-0.08	3.5 (5.9)	3.5 (4.9)	-0.01
Number of hospitalizations with PAD, mean (SD)	0 (0.1)	0 (0.2)	-0.04	0 (0.1)	0 (0.1)	0.01
Comorbid conditions, n (%)						
Atrial fibrillation	296 (17.4)	1195 (13.7)	0.10	290 (17.2)	296 (17.5)	-0.01

DREAM study protocol - Comparison 12 Pentoxifylline vs Cilostazol

Chronic obstructive pulmonary disease	557 (32.7)	2821 (32.4)	0.01	550 (32.6)	556 (33)	-0.01
Chronic liver disease	91 (5.3)	591 (6.8)	-0.06	89 (5.3)	89 (5.3)	0.00
Drug or alcohol abuse or dependence	282 (16.6)	2134 (24.5)	-0.20	281 (16.7)	284 (16.8)	-0.01
Heart failure	336 (19.8)	1320 (15.2)	0.12	329 (19.5)	335 (19.9)	-0.01
Hyperlipidemia	1309 (77)	7176 (82.5)	-0.14	1300 (77.1)	1303 (77.2)	0.00
Ischemic heart disease	792 (46.6)	4714 (54.2)	-0.15	784 (46.5)	783 (46.4)	0.00
Malignancy	508 (29.9)	2426 (27.9)	0.04	502 (29.8)	517 (30.6)	-0.02
Peripheral vascular disease	1646 (96.8)	8451 (97.2)	-0.02	1634 (96.9)	1635 (96.9)	0.00
Rheumatoid Arthritis	112 (6.6)	348 (4)	0.12	108 (6.4)	100 (5.9)	0.02
Renal dysfunction	478 (28.1)	2178 (25)	0.07	471 (27.9)	478 (28.3)	-0.01
Stroke or transient ischemic attack	241 (14.2)	1170 (13.5)	0.02	236 (14)	242 (14.3)	-0.01
Venous thromboembolism	132 (7.8)	410 (4.7)	0.13	128 (7.6)	125 (7.4)	0.01

9. Statistical analysis plans

Incidence rates for the outcome will be estimated for the treatment and reference groups before and after PS matching. The competing risk of death could be of concern for the current set of analyses if mortality is frequent among patients included in the cohort and if differences in the risk of mortality between treatment and reference groups are substantial. In the PS-matched sample, we will use cause-specific hazard models⁸ to provide hazard ratios averaged over the entire follow-up period as well as interval specific hazard ratios (1, 2, and 3 years) for the association between the treatment of interest and risk of ADRD after considering all-cause mortality as a competing event. Pre-specified subgroup analyses will be conducted based on age, sex, and baseline cardiovascular disease.

10. References

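### Two PAD claims do not show that PAD was the reason for starting either drug, and several diagnoses that could mark another reason are neither in the named covariates nor in the balance table

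*Combined protocol and SAP*

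**What the plan says.** Section 1a describes the population as "patients treated with Pentoxifylline versus cilostazol for peripheral artery disease (PAD"), so the active-comparator contrast assumes a shared indication. Section 5b puts that into practice with one criterion: "At least two claims with peripheral artery disease diagnosis recorded in 365 days prior to index date (ICD-9 or ICD-10 codes"). No rule links the prescription itself to a PAD diagnosis or deals with a competing reason for treatment. The flowchart in section 5c shows what the criterion removed, pooled over both drugs: "Excluded based on Peripheral artery disease Diagnosis -4,524 12,477".

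Section 6b lists the covariates. Among them are "Venous thromboembolism", rheumatoid arthritis, C-reactive protein tests and, under PAD treatments and severity indicators, "Critical limb ischemia". Section 8 reports balance for these and also for DMARD use, which 6b does not list. Neither section names chronic venous insufficiency, skin or venous ulcer, wound-care visits, vasculitis, or connective-tissue disease other than rheumatoid arthritis. The code definitions are in Appendix A, which is not part of the text available for this review.

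**The concern.** An active comparator controls confounding by indication only so far as both drugs are started for the same reason. Two PAD claims in a year fit PAD as the reason, but they also fit PAD that coexists with another leg, venous or inflammatory condition that prompted the prescription.

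The crude columns of section 8 give some cause to ask. The pentoxifylline arm has less coronary disease and fewer of several of its risk factors, yet more venous thromboembolism, rheumatoid arthritis, DMARD use and CRP testing. More severe arterial disease alone does not readily explain that combination.

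If a competing condition is more common among pentoxifylline initiators and also raises the chance of a recorded dementia diagnosis, the HR would mix the drug contrast with a difference in underlying disease. An upward bias could hide a small protective effect, which is what a repurposing study looks for. Balance on the listed covariates cannot settle the question: section 7 claims control of measured confounding only, and balance on rheumatoid arthritis is not evidence of balance on vasculitis.

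**Working it through.** **Inputs.** Counts are from section 8: crude denominators 1,701 (pentoxifylline) and 8,697 (cilostazol), matched 1,687 per arm. Flowchart counts are from section 5c.

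**1. Reproduce the plan's standardized differences.** d = (p1 − p0) / √{[p1(1 − p1) + p0(1 − p0)]/2}.

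For critical limb ischemia, p1 = 394/1,701 = 0.232 and p0 = 1,058/8,697 = 0.122, so d = 0.110/0.377 = 0.291 (stated 0.29). The other rows, done the same way:

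| Row | Crude % (pentoxifylline v cilostazol) | Crude d, recomputed (stated) | Matched d, stated |
|---|---|---|---|
| Smoking | 35.2 v 44.6 | −0.193 (−0.19) | 0.02 |
| Coronary artery disease | 47.0 v 55.1 | −0.161 (−0.16) | 0.00 |
| Lipid lowering drugs | 68.7 v 75.4 | −0.149 (−0.15) | 0.01 |
| Hyperlipidemia | 77.0 v 82.5 | −0.139 (−0.14) | 0.00 |
| Critical limb ischemia | 23.2 v 12.2 | 0.291 (0.29) | 0.00 |
| DMARD | 5.1 v 2.4 | 0.138 (0.14) | 0.00 |
| Venous thromboembolism | 7.8 v 4.7 | 0.126 (0.13) | 0.01 |
| Rheumatoid arthritis | 6.6 v 4.0 | 0.116 (0.12) | 0.02 |
| Stroke or TIA | 14.2 v 13.5 | 0.021 (0.02) | −0.01 |
| Peripheral vascular disease | 96.8 v 97.2 | −0.024 (−0.02) | 0.00 |
| Diabetes | 48.6 v 48.4 | 0.003 (0.00) | −0.04 |

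All agree with the table to rounding. CRP tests are stated as 0.13 crude and −0.02 matched; the one-decimal means and SDs give about 0.10 crude, which is within rounding. The antiplatelet row (24.2% v 100%) is not used: 100% in the cilostazol arm suggests that the index drug itself was counted.

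**2. Crude against matched.** Add critical limb ischemia, venous thromboembolism and rheumatoid arthritis, treating them as non-overlapping, which gives upper bounds:

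- Crude: (394 + 132 + 112)/1,701 = 638/1,701 = 37.5%, against (1,058 + 410 + 348)/8,697 = 1,816/8,697 = 20.9%.
- Matched: (381 + 128 + 108)/1,687 = 617/1,687 = 36.6%, against (380 + 125 + 100)/1,687 = 605/1,687 = 35.9%.

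The gap falls from 16.6 to 0.7 percentage points. Matching deals with the listed conditions. It also keeps 1,687/1,701 = 99.2% of pentoxifylline initiators, so patients with another indication, if there are any, have not been trimmed away.

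**3. The PAD criterion.** It removed 4,524/17,001 = 26.6% of those left at that step. Some of these may have had a single claim, and the count is not split by drug.

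**4. Possible size for an unlisted diagnosis.** The documents give neither its prevalence by arm nor its association with dementia, so all inputs here are assumptions. Bias factor = [1 + p1(HR − 1)] / [1 + p0(HR − 1)], a risk-ratio formula used as an approximation for the HR.

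- 15% v 10% after matching: HR 1.3 gives 1.045/1.030 = 1.015; HR 1.5 gives 1.075/1.050 = 1.024; HR 2.0 gives 1.15/1.10 = 1.045.
- 10% v 5%: HR 1.2 gives 1.02/1.01 = 1.010; HR 2.0 gives 1.10/1.05 = 1.048.
- Equal prevalence after matching: no bias.

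**The case against.** The strongest reply is that the analysed sample is the matched one, and there every row that raises the suspicion is balanced. Much of the route by which a competing illness could affect dementia is also measured: frailty score (0.21 crude, 0.02 matched), comorbidity score (0.18 to −0.02), falls, fractures, hospitalizations, outpatient visits and CRP tests. Prior nursing-home admission is an exclusion. Residual imbalance on the unlisted diagnoses could be close to nil. This largely stands. It limits the likely size, but it does not show balance on variables that nobody has tabulated.

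A reader might infer stronger things from the crude table, which the documents do not support:

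- **That venous disease is absent from the propensity score.** Venous thromboembolism is a listed covariate and is balanced. Only chronic venous insufficiency and venous ulcer are unnamed.
- **That pentoxifylline initiators have more ulcers.** There is no ulcer row. Critical limb ischemia is labelled a PAD severity indicator, so its excess may simply mean worse PAD, and whether its codes include ulceration cannot be judged without Appendix A.
- **That they have less atherosclerosis throughout.** Stroke/TIA, peripheral vascular disease and diabetes do not differ.
- **That the crude 37.5% v 20.9% contrast carries into the HR.** It becomes 36.6% v 35.9% after matching.

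Nor do the documents say that either drug is used for venous ulcer or vasculitis. The candidate diagnoses are proposed because they lie next to rows that differ, not because the plan states such use.

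**Conclusion.** The point holds in a limited form. Two PAD claims do not establish why the drug was started. The crude differences suggest that reasons may differ by arm, and a short list of related diagnoses is neither adjusted for directly nor shown to be balanced. This is possible residual confounding through unlisted conditions, not demonstrated confounding.

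Its size is unknown. On the assumed 15% v 10% after matching, the upward bias is about 1.5% to 4.5% for a dementia HR of 1.3 to 2.0. The direction assumes that the diagnosis is commoner in the pentoxifylline arm and raises recorded dementia. A wider assumed imbalance such as 20% v 8% would give 3.5% to 11% (1.06/1.024 to 1.20/1.08), but that supposes matching on correlated covariates helps little, and nothing in the documents supports it as an estimate. The conclusion also depends on Appendix A not already capturing these diagnoses under existing labels. The change is optional to modestly recommended, mainly because checking is cheap.

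**What to change.** 1. Check Appendix A. Unless existing codes already capture them, add to section 6b, measured in the 365 days before index: chronic venous insufficiency, chronic skin or venous ulcer, wound-care visits, and vasculitis or connective-tissue disease other than rheumatoid arthritis.
2. Re-estimate the propensity score, re-match, and report the crude and matched rows for these variables in section 8.
3. Split the 4,524 PAD-criterion exclusions by drug in section 5c. A clearly higher share in one arm would be direct, if partial, evidence on whether the indications differ.
4. As a sensitivity analysis, repeat analysis 1 without patients who have these competing-indication diagnoses. Do not restrict on critical limb ischemia: the plan treats it as PAD severity, so excluding it would test severity more than indication.

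The cost is a few code lists and a rerun on claims already held. A few matched pairs may be lost, and the interval will be wider in the sensitivity analysis only.

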Tricyclic antidepressants (TCAs)	Angiotensin converting enzyme inhibitors (ACEi)
Typical antipsychotics	Calcium channel blockers
Anticoagulants	Beta blockers
Antiplatelet agents	

Comorbid conditions	
Atrial fibrillation	Chronic liver disease
Coronary artery disease	Asthma
Heart failure	Ischemic heart disease
Stroke or transient ischemic attack	Chronic obstructive pulmonary disease
Peripheral vascular disease	Malignancy
Hyperlipidemia	Drug or alcohol abuse or dependence
Renal dysfunction	Venous thromboembolism
Rheumatoid Arthritis	Hypertension

Other PAD treatments and PAD severity indicators	
Critical limb ischemia Thrombolytic therapy (streptokinase, urokinase, alteplase, tissue plasminogen activator (tPA), pro-urokinase, reteplase, tenecteplase and Staphylokinase)	Number of cardiologist visits Number of hospitalizations with PAD

ICD-9, ICD-10, HCPCS, and NDC codes used to define the covariates listed above are available in Appendix A.

c. Outcome variables and study follow-up:

- **Primary outcome:** incident dementia, i.e., Alzheimer's disease, vascular dementia, senile, presenile, or unspecified dementia, or dementia in other diseases classified elsewhere. Outcome will be defined by 1 inpatient

claim or 2 outpatient claims in analysis 1, 2, 3. In analysis 4, the outcome will be defined by 1 inpatient or 1 outpatient claims and 1 prescription claim for a symptomatic treatment [donepezil, galantamine, rivastigmine, and memantine] within 6 months of each other with outcome date assigned to second event in the sequence.

- Secondary outcomes: Individual component:

Alzheimer's disease

Condition	ICD-9 and ICD-10 codes
Alzheimer's disease	331.0*, F00*, G30*
Vascular dementia	290.4*, F01*
Senile, presenile, or unspecified dementia	290.0*, 290.1*. 290.3*, 797*, F03*
Dementia in other diseases classified elsewhere	331.1*, 331.2*, 331.7*, 294.1*, F02*

For analysis 1,3, and 4 the follow-up will start the day after initiation of Pentoxifylline and Cilostazol and will continue until the earliest date of the following events:

- The first occurrence of the outcome of interest
- The date of end of continuous registration in the database,
- End of the study period,
- Measured death event occurs,
- The date of drug discontinuation, defined as the date of the last continuous treatment episode of the index drug (Pentoxifylline and Cilostazol) plus a defined grace period (i.e., 90 days after the end of the last prescription's days' supply in main analyses).

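### Lower-limb revascularisation and amputation are in neither the propensity score covariates nor the balance table, so prior procedures are not directly adjusted for and their matched balance cannot be seen

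*Combined protocol and SAP*

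**What the plan says.** Section 6b closes with a block headed "Other PAD treatments and PAD severity indicators". It has four items: critical limb ischaemia, thrombolytic therapy, and the two counts "Number of cardiologist visits Number of hospitalizations with PAD". Appendix A is cited for coding only: "codes used to define the covariates listed above are available in Appendix A". It is not said to add covariates.

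Section 7 fits the score "conditional on baseline covariates using multivariable logistic regression constructed separately in each data source" and states that "analyses conditioned on the PS provide effect estimates that are free from measured confounding".

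Section 8 gives these crude rows for the block (pentoxifylline, cilostazol, standardised difference):

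- "Critical limb ischemia 394 (23.2) 1058 (12.2) 0.29"
- "Thrombolytic therapy 10 (0.6) 26 (0.3) 0.04"
- "Number of hospitalizations with PAD, mean (SD) 0 (0.1) 0 (0.2) -0.04"
- cardiologist visits, mean 3.5 vs 4, difference -0.08

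No bypass, endovascular procedure or amputation appears in any block of 6b or in any row of section 8. Section 8 does carry at least one row that 6b does not list (DMARD), so both places were checked. Section 9 describes no bias analysis for factors outside the list.

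**The concern.** Both drugs are started for PAD, so confounding between them is likely to run partly through how severe the limb disease is and how it has already been managed. A previous revascularisation or amputation records both, and may also mark who was judged fit for a procedure. Either could plausibly relate to later dementia and to death, the competing event.

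The block's heading shows that the sponsor meant to control for other PAD treatments, but its contents hardly do so. The crude limb ischaemia row shows that the arms differ in limb severity before matching. A yes/no ischaemia code cannot separate patients who had a procedure from those who did not, and it cannot find procedures in patients without the code. Balance on that code is therefore no evidence of balance on procedures, and the table has no row in which a residual difference could be seen.

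**Working it through.** **1. Reproduce the plan's figures (section 8).** For proportions, d = (p1 − p2) / √{[p1(1 − p1) + p2(1 − p2)]/2}.

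- Critical limb ischaemia, crude: p1 = 394/1,701 = 0.2316 and p2 = 1,058/8,697 = 0.1217, so d = 0.1100/0.3774 = 0.291 (stated 0.29). Matched: 381 vs 380 of 1,687, d = 0.001 (stated 0.00).
- Thrombolysis, crude: 10/1,701 vs 26/8,697, d = 0.043 (stated 0.04). Matched: 9 vs 6, d = 0.027 (stated 0.03).
- Cardiologist visits, crude: (3.5 − 4)/√[(5.9² + 5.2²)/2] = −0.090 (stated −0.08, within rounding of the means). Matched: stated −0.01.
- Hospitalisations with PAD: the means print as 0, so −0.04 cannot be recomputed. A mean difference of 0.005 to 0.0075 would give −0.03 to −0.05, which is consistent. Matched: stated 0.01.

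One of the four items exceeds 0.1 before matching, and none does after.

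**2. How much the block can say about prior procedures.**

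- Thrombolysis, the only treatment: (10 + 26)/10,398 = 0.35%.
- Hospitalisations with PAD: the matched SD prints as 0.1, so it is below 0.15 and the variance is below 0.0225. For a count with mean m, the variance is at least m(1 − m). Hence m, and so the share of patients with any such admission, is at most about 2.3%.
- Critical limb ischaemia: 381 + 380 = 761 of 3,374 matched patients (22.6%) carry the code. The other 2,613 (77.4%) do not, and almost nothing else limb-specific describes them.
- Peripheral vascular disease, listed among comorbid conditions, is 96.9% in both matched arms and so barely discriminates.

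**3. Size of the possible bias.** The documents give neither the prevalence of procedures nor their relation to dementia, so every input here is an assumption. Let p1 and p0 be the prevalence in matched pentoxifylline and cilostazol patients, and RR the association with dementia given the covariates already matched. The factor on the observed ratio is approximately [1 + p1(RR − 1)] / [1 + p0(RR − 1)].

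| p1 vs p0 | RR 1.2 | RR 1.5 | RR 2.0 |
|---|---|---|---|
| 12.5% vs 10% | 1.005 | 1.012 | 1.023 |
| 15% vs 10% | 1.010 | 1.024 | 1.045 |
| 20% vs 10% | 1.020 | 1.048 | 1.091 |
| 23.2% vs 12.2% (crude ischaemia gap) | 1.021 | 1.052 | 1.098 |
| 30% vs 15% | 1.029 | 1.070 | 1.130 |
| 15% vs 30% | 0.972 | 0.935 | 0.885 |

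Example: 30% vs 15% with RR 2.0 gives 1.30/1.15 = 1.130. For scale, the largest gap printed among the matched percentages is 2.8 points (influenza vaccination, 60.8% vs 58%), close to the first line of the table.

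**The case against.** The strongest reply is that the plan already adjusts for much of what a procedure would mark. After matching, the composite frailty score goes from 0.21 to 0.02, the combined comorbidity score from 0.18 to −0.02, outpatient visits from 0.20 to −0.01, distinct prescriptions from 0.23 to 0.00 and smoking from −0.19 to 0.02. Coronary disease, diabetes, renal dysfunction, stroke and heart failure are also close. The new-user, active-comparator design with at least two PAD claims narrows the arms further. This stands: the adjustment is partial, not absent. A reader might infer that procedures are wholly unadjusted; that goes too far.

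A reader might also infer that the arms receive different PAD care. The table does not show it. The clearly imbalanced item is a marker of severity. The three treatment or use items differ by 0.04, −0.08 and −0.04 before matching, and all four lie between −0.01 and 0.03 after. Cardiologist visits may in any case reflect cardiac disease, since coronary artery disease is also more frequent in cilostazol initiators (55.1% vs 47%).

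The documents do not say that revascularisation is the main background treatment for PAD, and this point does not rely on it. The section 7 sentence on confounding covers measured factors only, so it is not contradicted. Appendix A is not in the text available here. If the ischaemia definition includes procedure codes, the gap would be smaller, although there would still be no separate row.

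Finally, a residual gap of 10 points or more after matching is generous, and matching on limb ischaemia probably shrinks it. This limits the size of the problem. It does not supply the missing diagnostic.

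**Conclusion.** The omission is a fact of sections 6b and 8: lower-limb revascularisation and amputation are not directly adjusted for, and their balance in the matched sample is unreported. It would be wrong to conclude that following the plan leaves the arms unbalanced on procedures; the balance is unknown.

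The likely bias is modest and its direction cannot be predicted. With assumed residual gaps of 5 to 15 points and associations of 1.2 to 2.0, it is about 1% to 13% on the ratio scale, either way. With a gap near 2.5 points it is about 0.5% to 2.3%. The case for acting is that limb-severity control rests mainly on one binary code with the largest crude imbalance in the table outside the antiplatelet row, and that the remedy is cheap. It does not show that the planned estimate is wrong.

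**What to change.** Before any outcome analysis:

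1. Add two baseline covariates to section 6b: lower-limb revascularisation (endovascular or surgical) and lower-limb amputation. Define each over the 365 days before the index date from procedure codes in the same Medicare claims, and put the code lists in Appendix A. A separate flag for the last 90 days is optional.
2. Put them in the propensity model, re-estimate the score and re-match.
3. Report both rows, crude and matched, in the section 8 table.

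If re-matching is not possible, the minimum is to report the balance of both in the existing matched sample and to add a bias analysis of the kind shown above, using the observed prevalences.

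The cost is the code lists, one re-run of the score, matching and balance table, and possibly a few of the 1,687 pairs. Parts A and B enrolment is already required throughout baseline and the plan already uses ICD and HCPCS codes, so no new data source is needed.
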